**STUDY INTERVENTION(S) / INVESTIGATIONAL AGENT(S):**

This prospective study will include approximately 25 patients with open-angle glaucoma who will undergo TCNR or trabeculectomy bleb by a glaucoma specialist at Northwestern Medicine. These patients will have a history of glaucoma and failed trabeculectomy bleb (as evidenced by clinical features and elevated IOP). During routine clinic visit, the patient will undergo lit lamp grading of bleb by Indiana Bleb Appearance Grading Score (IBAGS). Subjects who agree to participate and provide written informed consent will undergo AS-OCT imaging (Spectralis OCT, Heidelberg) of the bleb. During their operation, the Zeiss Artevo digital microscope integrated with iOCT (Zeiss Artevo 800, Carl Zeiss Meditec AG), a commercially available device will be utilized to visualize and evaluate the morphology of the trabeculectomy bleb at the start and conclusion of the case.

**PROCEDURES INVOLVED:**

The devices used in the study are commercially available and have been used extensively in ophthalmology and intraocular surgery. Therefore, no experimental devices will be used. The AS-OCT is routinely obtained and is considered standard of care. The iOCT is commercially available and is also utilized routinely in ophthalmic surgery, particularly for retinal surgery.

The Zeiss Artevo digital microscopy integrated with intraoperative OCT will be used as an adjunct to TCNR. Published research has not shown iOCT to increase risk of complications associated with routine TCNR and we believe injury from imaging is not biologically plausible. Surgery and iOCT will be recorded and saved to a secure NMH server. The surgical videos will only be used for research purposes.

Review of medical records will be performed for patients who agree to participate in the prospective study. Data gathered will include basic demographic information and clinical data relevant to glaucoma management (visual acuity, intraocular pressure, medications, disease

STU00213080

severity). Post-operative course including intraocular pressure, intraoperative or post-operative complications and repeat TCNR or additional surgery will also be collected.

Furthermore, a retrospective review of medical records will be performed for patients who underwent TCNR without iOCT or AS-OCT assistance by the same surgeon during the period from June 1, 2015 to June 1, 2020. This group of patients will serve as historical controls. These individuals will be identified using Enterprise Data Warehouse and billing data. We aim to identify approximately 25 controls. The selection criteria for controls are 1) age within 5 years of each study patient 2) same race as study patient 3) diagnosis of open angle glaucoma and 4) adequate follow up of at least 3 months.

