**OBJECTIVES:**

The aim of the research is to assess the surgical success, feasibility and utility of pre-operative Anterior Segment Optical Coherence Tomography (AS-OCT) and intraoperative Optical Coherence Tomography (iOCT) in trans-conjunctival needle revision (TCNR) of trabeculectomy bleb. Furthermore, we want to assess whether AS-OCT can be used to identify characteristics of trabeculectomy blebs that are associated with successful surgical outcomes.

To undergo this study, we will conduct a prospective study of patients who consent to AS-OCT and iOCT revision of TCNR. We will compare the outcomes of these patients with retrospectively identified, historical controls (i.e. patients who underwent TCNR by the same surgeon without AS-OCT or iOCT assistance).

We hypothesize that information gained from pre-operative AS-OCT and intraoperative OCT will aid with intraoperative decision-making for TCNR of trabeculectomy bleb and will thereby improve surgical outcomes. We also hypothesize that preoperative AS-OCT can be used to identify features of trabeculectomy bleb that can predict success with iOCT-assisted TCNR. More specifically, we hypothesize that filtering blebs with more extensive scarring as seen on pre-operative AS-OCT will benefit from iOCT.

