**STUDY ENDPOINTS:**

STU00213080

Results from the following tests obtained as part of this study:

1. Spectralis Anterior-segment OCT (AS-OCT) (Heidelberg Engineering) available in Lavin 15th floor Ophthalmology clinic
2. Digital microscope integrated with Intraoperative OCT (Zeiss Artevo 800, Carl Zeiss Meditec AG) available in the Lavin 11th floor operating room

The primary outcome will be surgical success, defined as a 20% reduction in unmedicated IOP below the pre-operative baseline at the post-operative visits (POD1, POM1, POM3). The success rate will be compared to a cohort of historical controls comprised of a consecutive series of age- and race-matched subjects who underwent TCNR in the operating room by the same surgeon, with the same intraoperative anti-fibrotic therapy, without AS-OCT or iOCT imaging during a five-year time period from 6/1/2015 to 6/1/2020.

The secondary outcomes will be feasibility and utility of intraoperative OCT. Feasibility will be defined as the percentage of cases with successful imaging of the bleb with iOCT. Utility will be defined as the percentage of cases in which iOCT changed surgical decision-making.

Intraoperative OCT will be used to determine whether adhesions have been completely lysed and/or whether further lysis of adhesions is necessary. A survey with set of questions based on prior literature will be used to assess these parameters.

We will also assess whether findings seen with pre-operative AS-OCT can predict what type of blebs will benefit from iOCT-assisted TNCR. Features of AS-OCT and iOCT imaging that will be assessed include quality of image capture, visualization of surgical site, and characteristics of the bleb. Characteristics of the surgical site include bleb height, internal reflectivity, location and number of adhesions, and presence of cysts, cavities, and fistulas.

STU00213080

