#### **PROVISIONS TO PROTECT THE PRIVACY INTERESTS OF PARTICIPANTS**

The study is done in the same facility that glaucoma clinic is located and patients are imaged with the AS-OCT device on the same floor. The acquired data with AS-OCT are similar to images routinely taken for their glaucoma follow up. The iOCT is attached to the operating microscope in the same operating room that is routinely used for ocular surgery. The consent process and

STU00213080

all the study procedures for individuals enrolled in the prospective study will be done in a private room/space.

To protect participant's confidentiality, their information and study conduct will only be discussed with individuals listed in the study personnel. Patients' data and all information pertaining to this study will remain confidential and all the study materials will be kept in a password-protected computer a password-protected file and a secure server. Paper files will be kept in a locked drawer.

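### The plan asks which blebs benefit from iOCT, but controls without AS-OCT images allow only a prognostic answer, and the control definition is worded inconsistently

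*Protocol*

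**What the plan says.** **The feature question.** Objectives contains two related statements. One is that pre-operative AS-OCT can identify bleb features that predict success with iOCT-assisted needling. The other, given as the more specific form, is that "filtering blebs with more extensive scarring as seen on pre-operative AS-OCT will benefit from iOCT". Study Endpoints repeats the second idea: AS-OCT findings are to show which type of bleb will benefit from iOCT assistance.

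**The controls.** Study Endpoints describes "a consecutive series of age- and race-matched subjects", operated on by the same surgeon "without AS-OCT or iOCT imaging during a five-year time period from 6/1/2015 to 6/1/2020". Objectives describes them as "patients who underwent TCNR by the same surgeon without AS-OCT or iOCT assistance", and Procedures Involved as "patients who underwent TCNR without iOCT or AS-OCT assistance by the same surgeon". Procedures Involved then lists four numbered selection criteria (age, race, open-angle glaucoma, at least 3 months of follow-up). None of them mentions AS-OCT. On number it says "We aim to identify approximately 25 controls".

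**The status of AS-OCT.** Procedures Involved states: "The AS-OCT is routinely obtained and is considered standard of care". The privacy section says "The acquired data with AS-OCT are similar to images routinely taken for their glaucoma follow up", and Sharing Results with Participants describes the results as part of standard care. Other sections treat the bleb AS-OCT as a study procedure. Under Study Intervention(s) it follows written consent. Recruitment Methods has patients already scheduled for surgery come back for study imaging. Economic Burden to Participants says the study AS-OCT is not billed.

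**The concern.** Whether an eye benefits from iOCT is a question about two outcomes at the same level of scarring: one with iOCT and one without. If controls have no AS-OCT, their scarring as AS-OCT would show it is unknown, and the second outcome is missing at every level. A feature that goes with success among the iOCT eyes may go with success equally when iOCT is not used. Reporting it as a marker of who benefits would be a wrong conclusion, and it could steer use of the device towards or away from the wrong eyes.

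The control wording matters for a separate reason. Two abstractors following different sections could select different eyes for the primary comparison, because an eye that was imaged but not operated on under that guidance is excluded by one section and admitted by two others.

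**Working it through.** There is no stated figure to reproduce. The 25 + 25 eyes are given without an error rate, power or success rates, so the check is mainly one of logic and text.

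**1. What the benefit hypothesis needs.** Let T and C be the success proportions with and without iOCT, at more or less scarring on AS-OCT.

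- Benefit at level s = T(s) − C(s).
- The scarring hypothesis concerns T(more) − C(more), and whether it exceeds T(less) − C(less).
- Four proportions are needed.

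**2. What the design supplies under the Study Endpoints wording.**

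- T(more) and T(less), from about 25 iOCT eyes.
- C(more) and C(less): 0 control eyes with AS-OCT features.
- Only the overall control rate is seen: C = w·C(more) + (1 − w)·C(less), where w, the share of more-scarred controls, is also unknown. One equation cannot fix two proportions, even if w were known.

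**3. Illustration with assumed proportions.** Take T(more) = 0.5, T(less) = 0.7 and w = 0.5 in both groups. The overall iOCT rate is 0.5 × 0.5 + 0.5 × 0.7 = 0.6. Suppose the overall control rate is 0.5, an overall difference of 0.1. All three rows below produce exactly these observed data.

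| C(more) | C(less) | Overall C | Benefit, more scarred | Benefit, less scarred |
|---|---|---|---|---|
| 0.3 | 0.7 | 0.5 | 0.5 − 0.3 = 0.2 | 0.7 − 0.7 = 0 |
| 0.4 | 0.6 | 0.5 | 0.5 − 0.4 = 0.1 | 0.7 − 0.6 = 0.1 |
| 0.5 | 0.5 | 0.5 | 0.5 − 0.5 = 0 | 0.7 − 0.5 = 0.2 |

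The within-arm contrast is 0.5 − 0.7 = −0.2 in every row. The rows support, in turn, benefit only in scarred blebs, equal benefit, and benefit only in unscarred blebs. More eyes would sharpen the −0.2 but would not tell the rows apart.

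**4. The control wording side by side.**

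| Place | Rule on AS-OCT | Eye imaged, image not used |
|---|---|---|
| Study Endpoints | no *imaging* | excluded |
| Objectives | no *assistance* | can be admitted |
| Procedures Involved, text | no *assistance* | can be admitted |
| Procedures Involved, four criteria | silent | admitted |

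The count of 0 control eyes with feature data therefore holds on the Study Endpoints wording. On the other wording the number is unknown, and the record review described for controls does not mention grading any images.

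**5. A conditional side calculation.** Let r be the share of 2015–2020 needlings with a pre-operative AS-OCT. It is not in the document, so every value here is assumed.

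- Eligible cases needed for 25 controls without AS-OCT, before matching = 25/(1 − r): 25 at r = 0, 25/0.5 = 50 at r = 0.5, 25/0.2 = 125 at r = 0.8.
- Suppose success differs by d between patients who would and would not be imaged, and the prospective arm has the mix r. The apparent arm difference with no true effect is r × d. For d of 10 to 20 points this is 5 to 10 points at r = 0.5 and 8 to 16 at r = 0.8, in either direction.

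At r near 0 both effects vanish.

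**The case against.** The strongest reply is that much of the feature aim needs no controls. Predicting success with iOCT-assisted needling is a within-arm question. Features can also be related to utility, which the plan defines as the share of cases in which iOCT changed a decision. This stands, and the restated aim below relies on it. It does not rescue the word *benefit*, because a changed decision is not a better outcome.

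A second reply is that the comparator suits the main hypothesis, which concerns information from AS-OCT and iOCT together. Controls with neither are the natural contrast. This also stands. Redefining controls by the absence of iOCT alone would admit eyes that had received part of the strategy and would change the question.

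A reader might go further and infer that the controls must be an atypical, biased group, since they lack a test the plan calls routine. The document does not support this. The standard-of-care sentence is a present-tense remark in a paragraph about device status and says nothing of this surgeon's practice in 2015–2020. The privacy section says only that the data are similar to routine images. The consent, recruitment and billing passages point to study imaging. The likelier defect is a loose sentence.

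**Conclusion.** The point holds as a mismatch between a stated hypothesis and the control definition. With controls taken as in Study Endpoints, AS-OCT features can be related to outcome only within about 25 iOCT eyes. That shows prognosis and cannot support a claim about which blebs benefit from iOCT. This rests on no numerical assumption; the proportions in the table only illustrate it. An analysis plan could not repair it, because the data would not exist.

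The conflict between *imaging* and *assistance*, and the silence of the numbered criteria, are textual facts to reconcile. The standard-of-care sentence needs clarifying against the sections that treat AS-OCT as study imaging. Selection bias in the primary comparison remains a possibility only if AS-OCT was in fact routine before needling in 2015–2020. The document does not say so, and the 5 to 16 points above are conditional on assumed values.

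The narrower aim, features that predict success with iOCT-assisted needling, is unaffected.

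**What to change.** 1. In Objectives and Study Endpoints, restate the feature aim and the scarring hypothesis as the association of AS-OCT features with success, and with iOCT utility, within iOCT-assisted needling. State that no conclusion about who benefits from iOCT will be drawn from it.
2. Use one control definition in Objectives, Study Endpoints and Procedures Involved, including the numbered criteria: needling not guided by AS-OCT or iOCT. This keeps the contrast with the combined strategy.
3. Record for each control whether a pre-operative bleb AS-OCT exists, and state whether AS-OCT was routine before needling in 2015–2020. If it was not, correct the standard-of-care sentence.
4. Only if stored control images exist and are comparable with the study images, add a feature-by-iOCT comparison, labelled exploratory.

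The cost is a narrower secondary claim, one extra abstraction variable and wording edits. Step 4, if taken, adds retrieval and grading of the control images, and with about 25 controls it would be imprecise.

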## **STUDY TIMELINES**

STU00213080

The participant will be in the study for the duration of their office visit (with AS-OCT testing) and surgery. In the context of this research study, participants will also be followed for 12 months after surgery to assess their post-operative course.

It will likely take approximately 12 months to enroll all study participants. The estimated date for completion of primary analyses will be 6 months after enrollment of study.

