### **Exclusion criteria**

- Age younger than 18 years;
- Secondary causes of glaucoma (e.g., iridocyclitis, trauma);

STU00213080

- Any evidence of corneal or conjunctival pathology adjacent to filtration bleb that could influence AS-OCT image
- Patients who did not undergo surgery or have adequate follow up
- Adults unable to consent, individuals who are not yet adults (infants, children, teenagers), pregnant women, prisoners and vulnerable populations

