### **WITHDRAWAL OF PARTICIPANTS**

All the participants are free to withdraw at any point of the study. In case the participants are not willing to continue with the study protocol they will be removed from the analysis.

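### Success is judged on unmedicated IOP alone, so an eye re-needled or re-operated before month 3 can count as a success of the index needling

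*Protocol*

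**What the plan says.** Protocol, Study Endpoints: the primary outcome is surgical success, "defined as a 20% reduction in unmedicated IOP below the pre-operative baseline at the post-operative visits (POD1, POM1, POM3"). The same section gives its use: "The success rate will be compared to a cohort of historical controls".

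Protocol, Procedures Involved, in the paragraph on prospective participants: "Post-operative course including intraocular pressure, intraoperative or post-operative complications and repeat TCNR or additional surgery will also be collected". The next paragraph sets the selection criteria for the historical controls. They cover age, race, diagnosis and "adequate follow up of at least 3 months", and do not mention a second procedure.

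Two other places decide who stays in the analysis. The Exclusion Criteria list "Patients who did not undergo surgery or have adequate follow up". Withdrawal of Participants says "In case the participants are not willing to continue with the study protocol they will be removed from the analysis". Study Timelines adds that "participants will also be followed for 12 months after surgery to assess their post-operative course".

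**The concern.** The trial's hypothesis, in the Objectives section, is that information from OCT "will aid with intraoperative decision-making for TCNR of trabeculectomy bleb and will thereby improve surgical outcomes". The outcome should therefore show whether the needling that imaging assisted controlled the pressure. An eye that needed a second pressure-lowering procedure was not controlled by the first.

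Requiring the pressure to be unmedicated keeps the effect of drugs from being credited to the index needling. Nothing does the same for a repeat needling or another glaucoma operation, which also lowers IOP. The definition can therefore count evidence against the index procedure as evidence for it.

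The comparison is with unrandomised historical controls treated between June 2015 and June 2020, so equal repeat rates in the two cohorts cannot be presumed. If such eyes are more frequent in one cohort, its success rate is raised relative to the other.

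**Working it through.** **Step 1. Does any section catch a re-treated eye?**

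- The Study Endpoints definition uses only unmedicated IOP against baseline.
- The Exclusion Criteria remove patients with no surgery or with inadequate follow-up. A re-treated eye has had surgery and may be fully followed.
- The withdrawal rule removes patients unwilling to continue. Accepting a second procedure is not unwillingness.
- The control criteria require follow-up, not freedom from re-intervention.

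No section fails, censors or removes the eye.

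**Step 2. Apply the definition to example eyes.** The protocol does not say whether the three visits are scored jointly or singly, so both readings are shown.

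| Course of the eye | All three visits must pass | Visits scored singly |
|---|---|---|
| Passes day 1, repeat, passes months 1 and 3 | Success | Success at months 1 and 3 |
| Passes day 1 and month 1, repeat, passes month 3 | Success | Success at month 3 |
| Passes day 1, fails month 1, repeat, passes month 3 | Failure | Success at month 3 |
| Fails day 1, repeat, passes months 1 and 3 | Failure | Success at months 1 and 3 |

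The gap exists on both readings. It is narrower if all visits must pass, because a failed visit before the repeat already makes the eye a failure.

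**Step 3. Size.** The protocol states no power, expected success rate or repeat rate, so there is no figure of its own to reproduce. Inputs are 25 prospective eyes (Study Summary and accrual table) and 25 control eyes (accrual table; Procedures Involved says approximately 25).

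- One eye in a cohort: 1/25 = 0.04, or 4 percentage points.
- With *a* such eyes in the imaged cohort and *b* in the controls, the difference shifts by (*a* − *b*)/25. A net of 0, 1, 2 or 3 eyes gives 0, 4, 8 or 12 points, in either direction.
- Unpaired standard error of the difference, with a common true rate *p* (assumed): √(2*p*(1 − *p*)/25). At *p* = 0.30 or 0.70 this is √0.0168 = 0.130; at *p* = 0.50 it is √0.02 = 0.141.
- One net eye is therefore 0.04/0.141 = 0.28 to 0.04/0.130 = 0.31 of a standard error. Three net eyes are 0.12/0.141 = 0.85 to 0.12/0.130 = 0.93.

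**Step 4. Two illustrations on assumed inputs.**

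- *Overstatement within one cohort.* Let *p* be the true index success rate, *r* the share of index failures re-treated before month 3, and *q* the share of those that then meet the criterion. If all such eyes are scored as successes (single-visit scoring), the overstatement is (1 − *p*)·*r*·*q*. With *p* 0.4 to 0.6, *r* 0.1 to 0.5 and *q* 0.5 to 0.7, it runs from 0.4 × 0.1 × 0.5 = 0.02 to 0.6 × 0.5 × 0.7 = 0.21, or 2 to 21 points. This is not the shift in the between-cohort difference.
- *Effect on a test.* With 18/25 against 10/25 successes, Fisher's exact test gives p = 0.045. If 3 of the 18 were re-needled eyes and counted as failures, 15/25 against 10/25 gives p = 0.258.

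**The case against.** The protocol never says that a re-operated eye is a success. It does not address the case, and handling of later procedures is often left to a statistical analysis plan, which is not at hand. Collection of repeat procedures is already planned, so the data for a rule would exist. The collection item does not show that early repeats are common: prospective follow-up runs to 12 months, and a repeat after month 3 cannot affect the outcome. The more natural reading of the visit list requires all three visits, which leaves a narrow route. The same definition and the same surgeon apply to both cohorts, so the shift may be zero, and even three net eyes stay below one standard error.

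Much of this stands. The narrower route under joint scoring is real, no direction of bias can be claimed, and the illustrations rest on chosen inputs.

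The appeal to the analysis plan does not succeed. What counts as surgical success is a clinical endpoint definition, and the protocol gives one in full. Applied as written, it gives the results in the table, and a later rule failing such eyes would change the stated endpoint. Collecting the data does not help while the outcome ignores them, and the explicit statement of collection covers only the prospective patients. A common definition protects the comparison only if repeats that end in a passing pressure are equally frequent in both cohorts, which an unrandomised design does not assure.

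**Conclusion.** The concern holds. On either reading of the visits, an eye given a second pressure-lowering procedure before month 3 can be scored as a success of the first. Each such eye raises its cohort's rate by 4 points, and each net eye moves the difference by 4 points, about 0.3 of a standard error. This assumes 25 eyes in each cohort, and the standard-error scale assumes true rates between 30% and 70% and an unpaired comparison. The actual counts cannot be derived from the protocol, so the size and direction of the bias are unknown. The endpoint should be corrected because the flaw is in the primary outcome and is cheap to close; no distortion of the comparison has been demonstrated.

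**What to change.** In Study Endpoints, add: *An eye with repeat TCNR or other IOP-lowering surgery after the index TCNR is a failure at every scored visit from the date of that procedure, in both cohorts.* This works whether the visits are scored jointly or singly, and leaves the handling of missed visits untouched.

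In Procedures Involved, state that the date of any such procedure through month 3 is abstracted in the same way for prospective eyes and historical controls.

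The cost is two sentences. The records are already under review, and the planned follow-up of both cohorts reaches month 3, so no new visits are needed. The downside is somewhat lower success rates in both cohorts.

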**VERSION DATE: 04/16/2021****STUDY SUMMARY:**

Investigational Agent(s) (Drugs or Devices)	N/A
IND / IDE / HDE #	
Indicate Special Population(s)	 Children  Children who are wards of the state  Adults Unable to Consent  Cognitively Impaired Adults  Neonates of Uncertain Viability  Pregnant Women  Prisoners (or other detained/paroled individuals)  Students/Employees
Sample Size	Prospective study: 25 Subjects  Retrospective study (historical controls): 25 subjects
Funding Source	Department of Ophthalmology  Illinois Society for the Prevention of Blindness
Indicate the type of consent to be obtained	 Written  Verbal/Waiver of Documentation of Informed Consent  Waiver of HIPAA Authorization  Waiver/Alteration of Consent Process

STU00213080

Site	 Lead Site ( For A Multiple Site Research Study)  Data Coordinating Center (DCC)
Research Related Radiation Exposure	 Yes  No
DSMB / DMC / IDMC	 Yes  No

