#### **CONSENT PROCESS**

Potential participants in the prospective study will be identified from the patients scheduled for follow up or surgery in the Glaucoma Service at Northwestern Medicine. Patients will be approached verbally about the study during their visits or over the phone by study approved personnel. The informed consent process will take place in person in a private room. The research team will go over the consent forms with the patients to ensure they understand the nature of the research study, its procedures, potential risks and benefits, and their responsibilities as participants. The patients will be given as much time as needed to consider the study and address any questions or concerns. If patients need additional time to decide whether or not to enroll in the study, they will have the option of rescheduling for a later time.

STU00213080

Throughout the consent process, the research team will stress that participation is completely voluntary and that participants may withdraw from the study at any point. Patients will be provided a copy of the fully executed, signed consent forms. An additional copy of the signed consent forms will be scanned into the patient's electronic medical record and hard copies will be maintained in the subject binder.

For the historical control data, a retrospective chart review of glaucoma patients who underwent TCNR surgery from June 1, 2015 to June 1, 2020, will be performed. Consent will not be obtained for these patients as they will not undergo any further testing or treatments.

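### The controls are called a consecutive matched series but set at about 25, with no rule for which charts are taken if more qualify; taking every eligible chart, listed before outcomes are read, closes that gap cheaply

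*Protocol*

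**What the plan says.** The primary comparison sets the success rate in the prospective arm against that of historical controls. Study Endpoints describes them as "a cohort of historical controls comprised of a consecutive series of age- and race-matched subjects", operated on in the operating room by the same surgeon with the same anti-fibrotic therapy and without OCT imaging, over five years.

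Procedures Involved gives the working rule: "We aim to identify approximately 25 controls". It continues: "The selection criteria for controls are 1) age within 5 years of each study patient 2) same race as study patient". The other two criteria are open-angle glaucoma and at least 3 months of follow-up. The charts are found by data-warehouse and billing search and concern operations "by the same surgeon during the period from June 1, 2015 to June 1, 2020".

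The Study Summary states the number without the qualifier: "Retrospective study (historical controls): 25 subjects". The accrual table for the historical controls also gives 25 adults and 25 eyes.

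The Consent Process section says of the controls: "Consent will not be obtained for these patients as they will not undergo any further testing or treatments".

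**The concern.** A consecutive series normally means every eligible case in order. A target of about 25, matched to the study patients, can mean a subset. The protocol names no start date within the window, no chronological order, no nearest-match rule and no random draw to settle which charts form that subset.

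This matters because of where the outcome sits. Success is derived from IOP at post-operative visits up to month 3, and a chart is accepted only if follow-up reaches 3 months. Confirming eligibility therefore takes the abstractor through the same period of the same record. No passage asks for the list to be fixed first, or for the person choosing to be unaware of IOP. With 25 controls, exchanging one failure for one success moves the control rate by 1/25 = 4 percentage points.

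A second, smaller matter is precision. If more than 25 charts qualify, stopping at 25 leaves usable control data aside, although each further control needs no consent, test or procedure.

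**Working it through.** **Plan's own figure.** The protocol gives 25 treated and about 25 controls, with no alpha, power, success rate or difference, so there is no calculation to reproduce. The success rates and pool sizes below are assumptions. All calculations treat the two groups as independent and ignore the matching.

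**Is a surplus of charts plausible?** Study Timelines expects about 12 months to enrol 25 patients, and the control window is 60 months. At the same pace, 25/12 × 60 = 125 procedures, before restriction to one surgeon, open-angle glaucoma, the same anti-fibrotic therapy, age, race and follow-up. This is an extrapolation. It shows only that more than 25 is possible.

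**Standard error.** With n = 25 treated, m controls and equal variances, the ratio to the 25 v 25 design is √[(1/25 + 1/m)/(2/25)].
- m = 50: √(0.0600/0.0800) = 0.866, a fall of 13%.
- m = 75: √(0.0533/0.0800) = 0.816, a fall of 18%.

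**Confidence interval.** The 95% half-width is 1.96 × √[p(1−p)/m + p(1−p)/25]. With p = 0.5 in both groups:
- m = 25: 27.7 points
- m = 50: 24.0 points
- m = 75: 22.6 points
- unlimited controls: 1.96 × √(0.25/25) = 19.6 points

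The 25 treated eyes set that floor.

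**Power.** Two-sided Fisher exact test at 0.05, by full enumeration of both binomials (treated v control success rate):

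| Assumed rates | 25 controls | 50 controls | 75 controls |
|---|---|---|---|
| 80% v 50% | 0.51 | 0.71 | 0.75 |
| 70% v 50% | 0.23 | 0.35 | 0.37 |

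Part of the jump from 25 to 50 controls comes from the discreteness of the Fisher test, whose actual size at 25 v 25 and 50% success is 0.033. The normal approximation gives 0.61, 0.73 and 0.78 for 80% v 50%, a gain of 12 points rather than 20 from 25 to 50 controls. For 70% v 50% it gives 0.30, 0.37 and 0.41.

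**If only about 25 charts qualify**, none of these gains arises.

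**The case against.** The strongest reply is that the sections can be read together. Study Endpoints puts matching and consecutiveness in one phrase, so taking matching charts in sequence until about 25 are reached would satisfy both it and Procedures Involved. That stands: this is not a flat contradiction. It does not supply the missing rule, because no starting point or direction is given and different starting points yield different sets of 25.

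A reader might infer that controls are hand-picked, one per patient, by someone looking at the result. The documents do not support that. They say the charts come from a database search under listed criteria, none of which is the IOP outcome. They state no one-to-one pick and do not say who chooses. What can be said is that selection with the outcome visible is possible and nothing prevents it.

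A reader might also infer that the plan discards eligible data. That is unproven too. Procedures Involved states an approximate aim, which may simply reflect the number the investigators expect to find, and the pool size is nowhere given. The 125 above borrows a hoped-for accrual rate and precedes every filter.

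The order of selection might be called a detail for a later document. However, this protocol itself fixes the number of controls and the criteria, and the proposal is to change that number.

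Finally, matching a small number of controls is a legitimate design for a small study, and covariate adjustment with 25 treated eyes can be unstable. Both points are fair, and they argue for keeping any adjustment simple.

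**Conclusion.** The point holds as a worthwhile, low-cost improvement. The protocol sets about 25 controls, calls them consecutive, and leaves open which charts are taken if more qualify, in a setting where eligibility and outcome are read from the same record. Taking all eligible charts, listed before outcomes are read, removes that choice whatever the pool size.

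The precision gain is conditional on the unknown pool. It is a 13% or 18% smaller standard error if 50 or 75 charts qualify under equal variances, and nil if about 25 do. The power gain from 0.51 to 0.71 or 0.75 belongs to a favourable assumed effect of 30 points. For 20 points, power stays below 0.4 by the exact test even with 75 controls, so the change does not make the study well powered for a moderate difference. It also leaves era effects, confounding and selection through the follow-up requirement untouched.

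**What to change.** In the Study Summary, Procedures Involved and the control accrual table, replace the target of about 25 with all TCNR eyes from 6/1/2015 to 6/1/2020 that meet the stated control criteria. Fix the list from the data-warehouse and billing query and the eligibility data (for follow-up, visit dates are enough) before any post-operative IOP is abstracted, and keep a dated copy. Handle age and race by variable-ratio matching or a simple adjustment, so that more than one control per study patient can be used.

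If the investigators prefer to keep about 25, the minimum is a stated start point and order, or a random draw, applied to the list before outcomes are read.

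The cost is more chart abstraction, a larger record count in the waiver request (and so wider use of identifiable records without consent), and an analysis that allows unequal group sizes. The prospective arm stays at 25, and no further patient is consented, tested or treated.
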